9.3.7 Time to Next Treatment

The time to next treatment (TNT) is defined as the time from the date of enrollment to the institution of next treatment.

10. DRUG INFORMATION

For nivolumab, please refer to the latest version of the prescribing information that can be found at <http://www.accessdata.fda.gov/scripts/cder/drugsatfda/>, and/or on the manufacturer's website.

For cabiralizumab, please refer to the current version of the Investigator's Brochure (IB) for additional information regarding this drug.

10.1 Cabiralizumab

Cabiralizumab (BMS-986227, FPA008) is a recombinant, humanized Immunoglobulin G4 (IgG4) monoclonal antibody that binds to human colony stimulating factor 1 receptor (CSF1R; c-fms). It is currently undergoing investigation in clinical trials, but has not yet been approved for commercial use.

10.1.1 Supplier/How Supplied

Bristol-Myers Squibb will supply cabiralizumab at no charge to subjects participating in this clinical trial. At the end of the study period, Bristol-Myers Squibb Company will not continue to supply study drug to subjects/investigators unless the Sponsor-Investigator chooses to extend their study. The investigator is responsible to ensure that the subject receives appropriate standard of care or other appropriate treatment in the independent medical judgement of the Investigator to treat the condition under study.

The investigator shall take responsibility for and shall take all steps to maintain appropriate records and ensure appropriate supply, storage, handling, distribution, and usage of investigational product in accordance with the protocol and any applicable laws and regulations.

10.1.2 Preparation

Solutions of cabiralizumab for IV infusion are prepared by dilution of the drug product in 0.9% sodium chloride or 5% dextrose injection. Since cabiralizumab solution contains no preservatives, diluted solutions for infusion should be administered or discarded within four hours after preparation. The IV administration set for cabiralizumab infusion must contain a 0.2 or 0.22 µm in-line filter or a 0.2 or 0.22 µm syringe filter.

10.1.3 Storage and Stability

Cabiralizumab drug product is shipped refrigerated at 2–8°C and stored refrigerated at 2–8°C until time of use. The contents of the vials supplied are sterile, pyrogen-free, and contain no preservatives. Vials are for single-use only. Drug product should be protected from light.

10.1.4 Handling and Disposal

Preparation should be performed by trained personnel in accordance with good practices rules, especially with respect to asepsis.

After final drug reconciliation, unused cabiralizumab should be disposed at the site following procedures for the disposal of anticancer drugs.

10.1.5 Dispensing

Cabiralizumab must be dispensed only from official study sites and to eligible subjects under the supervision of the site investigator. Cabiralizumab should be stored in a secure area according to local

regulations. It is the responsibility of the site investigator to ensure that study drug is only dispensed to subjects.

10.1.6 Adverse Events

Please refer to the most updated IB for a comprehensive list of adverse events. IB version 6 was used in preparation of this protocol.

The most common adverse events reported with cabiralizumab monotherapy include periorbital, facial, local and peripheral edema, pruritus, rash, and elevated lab values (CK, LDH, AST, ALT).

Hypersensitivity and/or infusion reaction is the most common toxicity with the use of monoclonal antibodies. There have been no infusion reactions or hypersensitivity reactions reported from any patients treated with cabiralizumab monotherapy to date while one patient in FPA008-003 that received cabiralizumab in combination with nivolumab experienced infusion reaction and another experienced a hypersensitivity reaction.

While no spontaneous infections in the nonclinical studies with cabiralizumab have been noted, macrophages play a role in innate immunity, and treatment with cabiralizumab may be associated with increased susceptibility to infections. Patients should be routinely monitored for signs and symptoms of infections during cabiralizumab treatment according to the clinical protocol.

In combination with nivolumab, the adverse event profile (other than infusion reactions as noted above) is similar to each agent individually.

10.2 Nivolumab

Nivolumab (also referred to as BMS-936558, MDX1106, or ONO-4538) is a human monoclonal antibody (HuMAb; immunoglobulin G4 [IgG4]-S228P) that targets the programmed death-1 (PD-1) cluster of differentiation 279 (CD279) cell surface membrane receptor. PD-1 is a negative regulatory molecule expressed by activated T and B lymphocytes.¹ Binding of PD-1 to its ligands, programmed death–ligands 1 (PD-L1) and 2 (PD-L2), results in the down-regulation of lymphocyte activation. Inhibition of the interaction between PD-1 and its ligands promotes immune responses and antigen-specific T-cell responses to both foreign antigens as well as self-antigens.

Nivolumab is approved in the United States for use in melanoma, non-small cell lung cancer, renal cell carcinoma, classical Hodgkin lymphoma, head and neck squamous cell carcinoma, and urothelial carcinoma.

10.2.1 Supplier/How Supplied

Bristol-Myers Squibb will supply nivolumab at no charge to subjects participating in this clinical trial. At the end of the study period, Bristol-Myers Squibb Company will not continue to supply study drug to subjects/investigators unless the Sponsor-Investigator chooses to extend their study. The investigator is responsible to ensure that the subject receives appropriate standard of care or other appropriate treatment in the independent medical judgement of the Investigator to treat the condition under study.

The investigator shall take responsibility for and shall take all steps to maintain appropriate records and ensure appropriate supply, storage, handling, distribution, and usage of investigational product in accordance with the protocol and any applicable laws and regulations.

10.2.2 Preparation

Nivolumab injection is to be administered as an IV infusion through a 0.2-micron to 1.2-micron pore size, low-protein binding (polyethersulfone membrane) in-line filter at the protocol-specified doses and infusion times. It is not to be administered as an IV push or bolus injection. Nivolumab injection can be infused undiluted (10 mg/mL) or diluted with 0.9% Sodium Chloride Injection, USP or 5% Dextrose Injection, USP to protein concentrations as low as 0.35 mg/mL.

During drug product preparation and handling, vigorous mixing or shaking is to be avoided. Care must be taken to assure sterility of the prepared solution as the product does not contain any antimicrobial preservative or bacteriostatic agent. Nivolumab infusions are compatible with polyvinyl chloride (PVC) or polyolefin containers and infusion sets, and glass bottles.

10.2.3 Storage and Stability

Vials of nivolumab injection must be stored at 2°C to 8°C (36°F to 46°F) and protected from light and freezing.

The administration of nivolumab infusion must be completed within 24 hours of preparation. If not used immediately, the infusion solution may be stored under refrigeration conditions (2°C to 8°C, 36°F to 46°F) for up to 24 hours, and a maximum of 8 hours of the total 24 hours can be at room temperature (20°C to 25°C, 68°F to 77°F) and room light. The maximum of 8 hours under room temperature and room light conditions includes the product administration period.

10.2.4 Handling and Disposal

Preparation should be performed by trained personnel in accordance with good practices rules, especially with respect to asepsis.

After final drug reconciliation, unused nivolumab should be disposed at the site following procedures for the disposal of anticancer drugs.

10.2.5 Dispensing

Nivolumab must be dispensed only from official study sites and to eligible subjects under the supervision of the site investigator. Nivolumab should be stored in a secure area according to local regulations. It is the responsibility of the site investigator to ensure that study drug is only dispensed to subjects.

10.2.6 Adverse Events

Please refer to the most updated IB for a comprehensive list of adverse events. IB version 16 was used in preparation of this protocol.

The overall safety experience with nivolumab, as a monotherapy or in combination with other therapeutics, is based on experience in approximately 16,900 subjects treated to date. The most common adverse events include pneumonitis, colitis, diverticular perforation, hepatitis, endocrinopathies (hypophysitis, thyroiditis, adrenal insufficiency), pancreatitis, asymptomatic amylase/lipase elevations,

rash, pruritus, nephritis, encephalopathy, aseptic meningitis, peripheral sensory/motor neuropathies (Guillain-Barre, myasthenia gravis), infusion reactions (rare), uveitis, and myopathy including myocarditis.

In combination with cabiralizumab, the adverse event profile appears similar to each agent individually.

11. ADVERSE EVENTS

11.1 Definitions

11.1.1 Adverse Event (AE)

An AE is any untoward medical occurrence whether or not considered related to the study drug that appears to change in intensity during the course of the study. The following are examples of AEs:

- Unintended or unfavorable sign or symptom
- A disease temporally associated with participation in the protocol
- An intercurrent illness or injury that impairs the well-being of the subject

Abnormal laboratory values or diagnostic test results constitute AEs only if they induce clinical signs or symptoms or require treatment or further diagnostic tests

Hospitalization for elective surgery or routine clinical procedures that are not the result of an AE (e.g., surgical insertion of central line) should not be recorded as an AE.

11.1.2 Serious Adverse Event (SAE)

An SAE is an adverse event that:

- Results in death. NOTE: Death due to disease progression should not be reported as a SAE, unless it is attributable by the site investigator to the study drug(s)
- Is life-threatening (defined as an event in which the subject was at risk of death at the time of the event; it does not refer to an event which hypothetically might have caused death if it were more severe)
- Requires inpatient hospitalization for >24 hours or prolongation of existing hospitalization. NOTE: Hospitalization for anticipated or protocol specified procedures such as administration of chemotherapy, central line insertion, metastasis interventional therapy, resection of primary tumor, or elective surgery, will not be considered serious adverse events.
- Results in persistent or significant disability/incapacity
- Is a congenital anomaly or birth defect
- Is an important medical event (defined as a medical event(s) that may not be immediately life-threatening or result in death or hospitalization but, based upon appropriate medical and scientific judgment, may jeopardize the subject or may require intervention (e.g., medical, surgical) to prevent one of the other serious outcomes listed in the definition above). Examples of such events include, but are not limited to, intensive treatment in an emergency room or at home for allergic bronchospasm; blood dyscrasias or convulsions not resulting in hospitalization; or the development of drug dependency or drug abuse.
- Is an overdose (defined as the accidental or intentional administration of any dose of a product that is considered by the treating physician as both excessive and medically important.) All occurrences of overdose must be reported as an SAE.

- Although pregnancy, overdose, potential drug-induced liver injury (DILI), and cancer are not always serious by regulatory definition, these events must be handled as SAEs.

11.1.3 Unexpected Adverse Event

For this study, an AE is considered unexpected when it varies in nature, intensity or frequency from information provided in the current IB, package insert, or when it is not included in the informed consent document as a potential risk. Unexpected also refers to AEs that are mentioned in the IB as occurring with a class of drugs or are anticipated from the pharmacological properties of the drug, but are not specifically mentioned as occurring with the particular drug under investigation.

11.1.4 Relatedness

AEs will be categorized according to the likelihood that they are related to the study drug(s). Specifically, they will be categorized using the following terms: Relatedness

Unrelated	The Adverse Event is not related to the drug(s)
Unlikely	The Adverse Event is doubtfully related to the drug(s)
Possible	The Adverse Event may be related to the drug(s)
Probable	The Adverse Event is likely related to the drug(s)
Definite	The Adverse Event is clearly related to the drug(s)

11.1.5 Pregnancy

If, following initiation of the study drugs, it is subsequently discovered that a subject is pregnant or may have been pregnant at the time of study drug exposure, including during at least 5 half-lives after study drug administration, the study drug will be permanently discontinued in an appropriate manner (e.g., dose tapering if necessary for subject safety).

The site investigator must immediately notify Big Ten CRC AHQ of this event via the SAE Submission Form in accordance with SAE reporting procedures. Big Ten CRC AHQ will then notify Worldwide Safety at BMS.

Protocol-required procedures for study discontinuation and follow-up must be performed.

Follow-up information regarding the course of the pregnancy, including perinatal and neonatal outcome and, where applicable, offspring information must be reported on the SAE Submission Form.

Any pregnancy that occurs in a female partner of a male study participant should be reported to Big Ten CRC AHQ via the SAE Submission Form in accordance with SAE reporting procedures. Big Ten CRC AHQ will then notify Worldwide Safety at BMS.

11.1.6 Drug Induced Liver Injury (DILI)

All occurrences of potential DILIs, meeting the defined criteria, must be reported as SAEs.

Potential drug induced liver injury is defined as:

1. An elevated AST or ALT lab value that is greater than $3 \times$ the upper limit of normal, **and**
2. an elevated total bilirubin lab value that is greater than $2 \times$ the upper limit of normal without initial findings of cholestasis (elevated serum alkaline phosphatase), **and**,
3. No other immediately apparent possible causes of aminotransferase (ALT or AST) elevation and hyperbilirubinemia, including, but not limited to, viral hepatitis, pre-existing chronic or acute liver disease, or the administration of other drug(s) known to be hepatotoxic.

DILIs that occur in any subject from the date of first dose through 100 days following discontinuation of dosing, whether or not related to the study drug, must be reported to Big Ten CRC AHQ within 24 hours/ 1 business day using the SAE Submission Form (see Documents/Info tab of the EDC). The form may be sent electronically to [contact]. Big Ten CRC AHQ will notify Worldwide Safety at BMS within 24 hours/ 1 business day.

11.2 Reporting

11.2.1 Adverse Events

- AEs will be recorded from time of signed informed consent until 100 days after discontinuation of study drug(s).
- AEs will be recorded regardless of whether or not they are considered related to the study drug(s).
- All AEs will be recorded in the subject's medical record and on the appropriate study specific eCRF form within the EDC system.
- All AEs considered related to study drug(s) will be followed until resolution to \leq Grade 1 or baseline, deemed clinically insignificant, and/or until a new anti-cancer treatment starts, whichever occurs first.
- Asymptomatic laboratory abnormalities that do not require treatment will not be collected as adverse events.

11.2.1.1 Big Ten CRC AHQ Requirements for Reporting AEs to Bristol-Myers Squibb

Adverse Events that are routinely collected according to Good Clinical Practice will be submitted to BMS every three (3) months by the last working day of the third month.

The Adverse Event information required to be sent to BMS as noted in the 'Bristol-Myers Squibb Early Asset Investigator Sponsored Research (ISR) Import Plan.' This document describes the method of collection and submission to BMS via the mailbox:

[contact]

When the file is submitted to BMS, it will be noted that the file contains non-serious AEs not previously submitted to BMS within the previous 3 months.

11.2.2 Serious Adverse Events (SAEs)

11.2.2.1 Site Requirements for Reporting SAEs to Big Ten CRC Administrative Headquarters

- SAEs will be reported from time of signed informed consent until 100 days after discontinuation of study drug(s).

- SAEs will be reported on the SAE Submission Form and entered in the SAE tab in the EDC system **within 1 business day** of discovery of the event.
- SAEs include events related and unrelated to the study drug(s).
- All SAEs will be recorded in the subject's medical record and on the appropriate study specific eCRF form within the EDC system.
- All SAEs regardless of relation to study drug will be followed until resolution to \leq Grade 1 or baseline and/or deemed clinically insignificant and/or until a new anti-cancer treatment starts, whichever occurs first.

The site will submit the completed SAE Submission Form (see Documents/Info tab of the EDC) to Big Ten CRC AHQ within **1 business day** of discovery of the event. The form may be sent electronically to [contact]. If only limited information is initially available, follow-up reports are required.

The site investigator is responsible for informing the IRB and/or other local regulatory bodies of the SAE as per local requirements.

The original copy of the SAE Submission Form and the email correspondence must be kept within the study file at the study site.

If an ongoing SAE changes in its intensity, relationship to study drug, or if new information becomes available, sites must submit a follow up SAE Submission Form within 1 business day to Big Ten CRC AHQ electronically at [contact]. (Note: Follow-up SAE reports should include the same investigator term(s) initially reported.)

11.2.2.2 Big Ten CRC AHQ Requirements for Reporting SAEs to Bristol-Myers Squibb

Big Ten CRC AHQ will report all SAEs, regardless of relationship to study drug, to Bristol-Myers Squibb within 24 hours/1 business day of receipt of the SAE Reporting Form. Follow-up information will be provided to Bristol-Myers Squibb as reasonably requested.

SAE Email Address: [contact]

SAE [contact]

Follow-up SAE reports will be sent by Big Ten CRC AHQ within 24 hours/1 business day to BMS (or designee) using the same procedure used for transmitting the initial SAE report.

SAE Reconciliation:

On behalf of the Sponsor Investigator, Big Ten CRC AHQ will ensure that all SAEs in the clinical database are reported to BMS and any applicable health authority during the conduct of the study. This reconciliation will occur at least quarterly and be initiated by Big Ten CRC AHQ. Big Ten CRC AHQ will request a reconciliation report from: [contact]. During reconciliation, any events found to not be reported previously to BMS must be sent to [contact].

All SAEs should be faxed or emailed to BMS at:

Global Pharmacovigilance & Epidemiology

Bristol-Myers Squibb Company

[contact]

Email: [contact]

11.2.2.3 Sponsor-Investigator Responsibilities

Big Ten CRC AHQ will send a SAE summary to the sponsor-investigator and the Michigan Institute for Clinical and Health Research (MICHHR) IND/IDE Investigator Assistance Program (MIAP) **within 1 business day** of receipt of SAE Submission Form from a site. The sponsor-investigator will promptly review the SAE summary and assess for expectedness and relatedness.

11.2.2.4 Michigan Institute for Clinical and Health Research (MICHHR) IND/IDE Investigator Assistance Program (MIAP) Responsibilities for Reporting SAEs to FDA

MICHHR-MIAP is responsible for managing the Investigational New Drug Application (IND) associated with this protocol on behalf of the sponsor-investigator. Big Ten CRC AHQ will obtain a copy of the cross-reference letter(s) from Bristol-Myers Squibb and provide to MICHHR-MIAP for the IND application ([contact]). MICHHR-MIAP will cross-reference this submission to Bristol-Myers Squibb's parent IND at the time of submission. MICHHR-MIAP will provide Big Ten CRC AHQ with a copy of the application and Big Ten CRC AHQ will provide a copy of these documents to Bristol-Myers Squibb.

MICHHR-MIAP will be responsible for all communication with the FDA in accordance with 21CFR312 which includes but is not limited to the 7 and 15 Day Reports, as well as an Annual Progress Report. MICHHR-MIAP will provide Big Ten CRC AHQ with copies of any FDA communication. Big Ten CRC AHQ will provide a copy of these reports to Bristol-Myers Squibb as required per contract.

11.2.2.5 IND Safety Reports Unrelated to this Trial

Bristol-Myers Squibb will provide Big Ten CRC AHQ with IND safety reports from external studies that involve the study drug(s) per their guidelines. Big Ten CRC AHQ will forward the safety reports to the sponsor-investigator who will review these reports and determine if revisions are needed to the protocol or consent. Big Ten CRC AHQ will forward these reports to participating sites **within 1 business day** of receiving the sponsor-investigator's review. Based on the sponsor-investigator's review, applicable changes will be made to the protocol and informed consent document (if required). Any changes made to the protocol and/or informed consent document will be submitted to the FDA by MICHHR-MIAP. All IND safety reports will also be made available to sites via the EDC system.

Upon receipt from Big Ten CRC AHQ, site investigators (or designees) are responsible for submitting these safety reports to their respective IRBs, as per their IRB policies.

12. STATISTICAL METHODS

12.1 Study Design

This is a phase II single arm, non-randomized, open label trial with an interim futility/safety analysis.

12.2 Endpoints

12.2.1 Definition of Primary Endpoints

See Section 9.3.

12.2.2 Definition of Secondary Endpoints

See Section 9.3

12.3 Sample Size, Accrual, and Interim Futility Analysis

We propose a two-stage design with co-primary endpoints of complete response (CR) and overall response (OR), testing a “both-and” null hypothesis against an “either-or” alternative hypothesis. Specifically, we posit that a CRR of 30% or ORR of 60% is achievable (note that CRR refers to the *marginal* CRR, that is, the complete response rate without respect to overall response status, and not the *conditional* CRR, which would be the complete response rate among any responders). Initially, 17 eligible patients will be followed for response. At this point, if fewer than 3 patients demonstrate CR (<18%) and fewer than 7 patients demonstrate OR (<41%), the trial will be stopped for futility.

Otherwise, we will enroll an additional 16 patients, and the trial will successfully conclude if at least 7 patients (out of 33 total) demonstrate CR (21%) or at least 17 patients demonstrate OR (52%).

We will also formally incorporate three Grade 4+ adverse event (AE) thresholds that will activate at the interim analysis. First, if the number of patients with any Grade 4 AE is greater than or equal to 7 (7/17=41%) by the interim analysis, enrollment will stop. Second, if the number of patients with Grade 4 AEs that *require discontinuation of study treatment, as specified in section 6.3*, is greater than or equal to 3 (3/17=12%) by the interim analysis, enrollment will stop. Third, enrollment will stop at the interim analysis for any Grade 5 AE attributable to drug.

To demonstrate the operating characteristics of this design, we simulated repeated trials under a grid of different true values of CRR, ORR, and Grade 4+ AE rate. When the true CRR and ORR are simultaneously no greater than 10% and 30%, respectively, and the true Grade 4+ AE rate is 32%, this design will successfully conclude with probability less than 0.05 (one-sided type I error) and stop (for futility or safety collectively) at the interim analysis with probability about 0.75. When the true CRR is at least 30% or the true ORR is at least 60%, this design will successfully conclude with probability at least 0.62 (power) and stop at the interim analysis with probability at most 0.34. The schematic in Figure 1, immediately below, gives the full operating characteristics over all considered combinations of CRR and ORR when the true Grade 4+ AE rate is 32%. The blue-purple region denotes the true generating scenarios satisfying the ‘either-or’ hypothesis, wherein at least one of the efficacy thresholds is met or exceeded. The green region denotes satisfying neither the null nor the alternative hypothesis, wherein both efficacy rates exceed their null values but neither meets the alternative. The red region denotes the ‘both-and’ null hypothesis.

[figure not shown]

Figure 1: Probability of declaring success and, in parentheses, probability of stopping at the interim analysis for futility or toxicity, when the true Grade 4+ AE rate is 32%.

To demonstrate the effect of our toxicity stopping rule, Figure 2 below gives the operating characteristics of our design when the true Grade 4+ AE rate is 50%. The entire region is shaded red, because the treatment regimen is unacceptably toxic. The probability of declaring success, even when one of the efficacy thresholds is satisfied in truth, is always less than 0.16, and the trial stops at the interim analysis with probability at least 0.83.

[figure not shown]

Figure 2: Probability of declaring success and, in parentheses, probability of stopping at the interim analysis for futility or toxicity, when the true Grade 4+ AE rate is 50%.

Peripheral T-cell lymphoma response and progression will be assessed using the LYRIC criteria as outlined in section 9.

Safety assessments will consist of the surveillance and recording of AEs and documentation of physical examination findings and laboratory data. Type, incidence, severity, seriousness, and relatedness of adverse events will be recorded. Additional secondary analyses include PFS, DCR, DOR, and TNT.

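### Stopping rule 1 is worded as Grade 4 but its stated properties are for a Grade 4+ count, and the synopsis and section 12.3 disagree on whether an unattributed fatal AE stops enrollment

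*Combined protocol and SAP*

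**What the plan says.** Section 12.3 introduces the safety rules this way: "We will also formally incorporate three Grade 4+ adverse event (AE) thresholds that will activate at the interim analysis". The interim is set at 17 patients: "Initially, 17 eligible patients will be followed for response".

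- **Rule 1:** "First, if the number of patients with any Grade 4 AE is greater than or equal to 7" of the 17 (41%) at the interim, enrollment stops.
- **Rule 2:** "Second, if the number of patients with Grade 4 AEs that" call for discontinuation under section 6.3 reaches 3, enrollment stops.
- **Rule 3:** "Third, enrollment will stop at the interim analysis for any Grade 5 AE attributable to drug".

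The synopsis (Statistical Considerations) also words rules 1 and 2 as grade 4. Its rule 3 differs: one Grade 5 AE among the first 17 subjects stops enrollment, with no condition on attribution.

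The properties of the design come from simulation: "we simulated repeated trials under a grid of different true values of CRR, ORR, and Grade 4+ AE rate". Results are reported for Grade 4+ rates of 32% and 50%. At 50%, which section 12.3 treats as unacceptably toxic, "the trial stops at the interim analysis with probability at least 0.83" and the probability of declaring success is below 0.16. At 32% with an effective regimen, power is stated as at least 0.62 and the stop probability as at most 0.34.

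**The concern.** The heading of the rules and the simulation both speak of Grade 4+, while rules 1 and 2 as written count Grade 4 only. In section 12.3, Grade 5 enters solely through rule 3, and only when attributed to drug. A patient with an unrelated Grade 4 AE therefore counts toward rule 1, while a patient whose only severe event is an unrelated fatal AE counts toward nothing. If such patients occur, rule 1 as written is less sensitive than the rule whose properties are printed, in the scenario where it is most needed. Someone applying the synopsis would reach the opposite decision on the same patient.

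**Working it through.** **Inputs.** From section 12.3: 17 patients at the interim and 33 in total; rule 1 threshold 7; rule 2 threshold 3; futility stop if CR < 3 and OR < 7 of 17; success if CR ≥ 7 or OR ≥ 17 of 33; Grade 4+ rates 32% and 50%. Not in the documents, so assumed: how the Grade 4+ rate divides into Grade 4, attributable Grade 5 and unattributed Grade 5, and the share of Grade 4 patients who must discontinue. Toxicity and response are taken as independent.

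**Step 1: reproduce the stated figures.** Apply rule 1 alone to all Grade 4+ patients: T(p) = P(Bin(17, p) ≥ 7). This gives T(0.50) = 0.834 and T(0.32) = 0.284. For efficacy, use an exact trinomial (CR, PR, neither) over stages of 17 and 16. F is the probability of a futility stop and S the probability of efficacy success ignoring toxicity. Then stop = 1 − (1 − F)(1 − T) and success = S(1 − T).

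| Grade 4+ rate | CRR / ORR | F | S | Stop | Success | Stated |
|---|---|---|---|---|---|---|
| 32% | 10% / 30% | 0.649 | 0.042 | 0.749 | 0.030 | about 0.75; < 0.05 |
| 32% | 30% / 30% | 0.077 | 0.867 | 0.339 | 0.621 | at most 0.34; at least 0.62 |
| 50% | 30% / 60% | 0.014 | 0.955 | 0.836 | 0.159 | at least 0.83; < 0.16 |

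The printed figures match rule 1 on a Grade 4+ count, with no visible contribution from rule 2 or rule 3.

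**Step 2: rule 1 as written.** Let u be the part of the 50% made up of patients whose only Grade 4+ event is an unattributed Grade 5 AE. With rules 2 and 3 adding nothing, the stop probability from the safety rules is T(0.50 − u).

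| u (points) | 0 | 1 | 2 | 5 | 10 |
|---|---|---|---|---|---|
| Section 12.3 wording | 0.834 | 0.812 | 0.789 | 0.710 | 0.552 |

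With the synopsis version of rule 3, which stops for one such event, 2, 5 and 10 points give 0.866, 0.905 and 0.949.

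**Step 3: all three section 12.3 rules active at 50%.** Let d and g be the probabilities of Grade 4 with and without required discontinuation, a that of attributable Grade 5 only, and r = 1 − d − g − a. No safety stop requires no attributable Grade 5, at most 2 discontinuing and at most 6 Grade 4 patients in all:

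stop = 1 − Σ(D = 0..2) Σ(G = 0..6−D) [17! / (D! G! (17−D−G)!)] d^D g^G r^(17−D−G).

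- u = 3 points, a = 2 points, 30% of Grade 4 patients discontinuing: d = 0.135, g = 0.315, r = 0.53; stop = 0.848.
- u = 10 points, a = 2 points, 40% discontinuing: d = 0.152, g = 0.228, r = 0.60; stop = 0.762.
- With u = 2 points and a = 0, the stop probability returns to 0.834 once about 31% of Grade 4 patients discontinue. With u = 5 or 10 points, it takes about 45% or 59%.

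**Step 4: the same rules at 32%.** With no Grade 5 and 20% of Grade 4 patients discontinuing, d = 0.064, g = 0.256, r = 0.68, and the safety stop is 0.320. At CRR 30% / ORR 30%, stop = 1 − (1 − 0.0774)(1 − 0.3198) = 0.372 and power = 0.8674 × (1 − 0.3198) = 0.590. These miss the stated limits of 0.34 and 0.62.

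**The case against.** The strongest reply is that the synopsis already covers the case: its rule 3 stops for one Grade 5 AE whatever its cause, and under that text the 0.83 floor holds for every split. That is correct for the synopsis. It does not settle the matter, because section 12.3, where the operating characteristics are given, adds the attribution condition and so gives the opposite answer.

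A reader might infer that the 0.83 is simply not delivered. The documents do not support that. They give no split, and step 3 shows that rules 2 and 3 can restore 0.83 in some cases and not in others. The sponsor cannot, however, rely on rule 2 at 50% and ignore it at 32%, where step 4 shows that it breaks the printed limits.

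A reader might also infer that rule 2 was simulated on Grade 4+ events and needs the same rewording. Nothing shows this: section 12.3 states no discontinuation rate for the simulation, and rule 1 alone accounts for the figures.

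Nor does the median survival below 6 months quoted in section 1.3 establish that such deaths will be frequent. Section 11.1.2 keeps deaths from progression out of SAE reporting unless they are attributed to study drug. Section 11.1.4 has a possible category, so an uncertain death may count as attributable. A fatal case with an earlier Grade 4 AE is already in the rule 1 count. The gap concerns patients whose only Grade 4+ event is a death judged not attributable.

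**Conclusion.** The point stands in two parts. First, rule 1 as written (Grade 4) is not the rule whose properties are stated (Grade 4+). Second, the synopsis and section 12.3 contradict each other on rule 3. The effect on the 50% stop probability is conditional: from 0.834 with no affected patients down to 0.55 with 10 points affected, if rules 2 and 3 add nothing, and 0.83 or above where they add enough. Separately, the printed stop probability and power at 32% fit only if rules 2 and 3 contribute nothing. All of this rests on independence of toxicity and response and on assumed splits. It should be corrected, but it does not call for a change in sample size or in the threshold of 7.

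**What to change.** 1. In the synopsis and section 12.3, word rule 1 as patients with an AE of Grade 4 or higher. Its 0.834 at a 50% rate then holds for any Grade 4/5 split. Section 11.2.1 already records AEs regardless of relatedness, so the data will exist.
2. Reconcile the two versions of rule 3 so that both places treat a Grade 5 AE not attributed to drug in the same way.
3. Restate the stop probability and power at 32% and 50% with all three rules active, giving the assumed Grade 4/5, attribution and discontinuation split and a range around it.

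The wording of rule 2 need not change for this purpose. The cost is a short edit in two places and a short re-simulation. The wording alone does not make every printed figure true: once rules 2 and 3 are included, some of the figures at 32% may become less favourable.
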